7. ADVERSE EVENT REPORTING

In accordance with VUMC policy, adverse events and unanticipated problems involving risk to participants or others that fall under VUMC IRB jurisdiction will be reported to the VUMC IRB within 10 working days after learning of the event or problem.

8. DATA AND SAFETY MONITORING

The PI ([name]) will form a data and safety monitoring board (DSMB) to overview the study, including safe keeping of stored data and monitoring/supervising research staff in the responsible conduct of research. The DSMB will have content experts and an independent biostatistician to review study progress and any adverse events. Experts include VUMC faculty with expertise in biostatistics, the provision of clinical trials with psychosocial interventions, integrative medicine, and pain psychology. Safety after sensory testing will be the responsibility of the research team member present with the participant and CRC nurse. This testing procedure will be conducted in a clinical setting with physicians and staff on site. Should safety concerns arise during the study, [name] will be responsible for immediately notifying the treating physician. [name] will also be responsible for monitoring safety of participants involved in the self-management intervention or attention control conditions. Should concerns arise with the emotional stability of a participant or a potential participant (during recruitment), [name] will follow the above procedures and also notify treating physicians as needed. The DSMB for the study will be updated monthly regarding any adverse events and convene annually to review study progress. As required by the institution and IRB, any adverse events will be reported to the IRB within 10 days.

9. STATISTICAL CONSIDERATIONS

9.1 Analytic Plan by Aim

Aim 1: To construct a patient-centered CBT self-management (SM) intervention specific to IC/BPS. Pre-work for this aim will include a theme analysis of coded transcripts from focus groups using NVivo 9 to code, analyze, and interpret transcripts using elements of grounded theory.⁷⁸ For the project period, this aim will primarily involve consolidating qualitative work and will use descriptive statistics where appropriate.

Aim 2: To obtain preliminary data comparing the effectiveness of integrating SM interventions into usual treatment (N = 50) to control (AC, N = 25) in improving targeted primary (symptom improvement [≥ 7 point reduction in GUPI]) and secondary (pain, distress, quality of life) outcomes.

Power and sample size considerations: ■ are comparing GUPI-Total Score, a continuous variable, between the SM group and a matched AC group with a 2:1 randomization scheme. The GUPI-Total Score tends to be normally distributed with a standard deviation of 8.61.^{47,79} A 7-point decrease in total GUPI score is considered clinically meaningful⁷⁹ and a robust assessment of response to treatment.⁴

Assuming a Type I error of 0.05 and power of .90, we will need 50 experimental subjects and 25 control subjects to reject the null hypothesis that the sample means of both treatment groups are equal post-treatment. ■ intend to have 50 experimental and 25 control subjects to obtain even groups for analytical purposes, as recommended by ■ DSBM. Given our use of statistical models, ■ power is increased when ■ appropriately adjust for covariates.

■ will test the hypothesis that those receiving the SM intervention will show improved outcomes relative to AC. ■ will use generalized linear mixed models to compare responses on the Genitourinary Pain Index (GUPI⁸⁰-Primary Outcome) between treatment groups, adjusting for baseline GUPI and covariates. As recent evidence recommends the examination of pain and urinary symptoms separately,²⁵ ■ will examine the GUPI pain subscale and GUPI urinary subscale separately in secondary analyses. ■ will perform one interim analysis at approximately 50% completion of data collection using the O'Brien-Fleming method to preserve alpha accounting for repeat testing.

■ will examine changes in secondary outcomes of interest, including pre- to post-treatment changes in emotional distress (e.g. PHQ-8, GAD-7, PCL-5, CSQ), quality of life and wellness (e.g. PROMIS-29), widespread pain (MBM/Choir bodymap), and perceived treatment benefit (PGI) using similar approaches: linear models for continuous outcomes, proportional odds models for ordinal outcomes, and logistic models for binary outcomes. As ■ training in data analysis progresses, ■ will apply more sophisticated approaches, such as hierarchical modeling. As ■ anticipate potential confounding from factors such as age and time since diagnosis, we will account for these as covariates in the analyses. Further, as opiate use is associated with increased pain sensitivity and decreased pain thresholds on psychophysical testing,⁷³ ■ will stratify groups by opiate use during randomization. ■ will additionally consider opiate use as a covariate in the analyses. To address sex as biologic variable, we will examine sex as a moderator of treatment effects, since men and women perceive pain differently in self-report⁷⁴ and sensory testing.⁸¹

Aim 3: To determine whether patient phenotype moderates treatment response to a SM intervention. As an exploratory aim, ■ will assess the hypotheses that a) higher pre-treatment psychological distress, b) higher baseline temporal summation, and c) number of chronic overlapping pain conditions will be associated with greater SM treatment efficacy. To avoid loss of power from testing a phenotype x treatment x time interaction, ■ will model the change in GUPI and treatment response (PGI) using a proportional odds model adjusted for baseline GUPI, and test for a treatment x phenotype interaction. A positive finding would suggest treatment effects depend on these moderating factors. ■ increased our sample size for this analysis by applying a 2:1 randomization scheme; however, given that our treatment group still constitutes a small sample size (n=50), ■ will set a threshold of p<.2 for the interaction before proceeding with a responder or mediation analysis. ■ will use these analyses to identify factors needing consideration in future studies expanding the generalizability of SM.

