5.6.3 Fidelity monitoring

The PI will oversee intervention training and delivery by adhering to NIH Behavioral Change Consortium guidelines⁴² recently reviewed as applied to clinical pain trials in Edmond (2018).⁴³ This will include structured training in intervention delivery, recording of sessions, and the PI engaging in weekly supervision with trial therapists to review content summary guide checklists and session material.

Clinical assessments

The battery of assessments below will be given at pretreatment, posttreatment, and at the three-month follow-up mark. Assessments will be completed in two stages at each timepoint: 1) online patient reported outcome measures and 2) in person psychophysiological testing and the collection of biological samples.

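### Continuous secondary outcomes are specified as pre- to post-treatment change, and no model names the outcome's own baseline as a covariate, although that baseline is collected

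*Combined protocol and SAP*

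**What the plan says.** Section 9.1 (Aim 2) treats the primary and secondary outcomes differently in what it writes down.

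- **Primary outcome.** GUPI is compared "between treatment groups, adjusting for baseline GUPI and covariates".
- **GUPI pain and urinary subscales.** They are to be examined separately in secondary analyses. Neither a change score nor a subscale baseline is mentioned.
- **Other secondary outcomes.** The sponsor "will examine changes in secondary outcomes of interest, including pre- to post-treatment changes in emotional distress (e.g. PHQ-8, GAD-7, PCL-5, CSQ", and also PROMIS-29, the body map and PGI. The methods are described as like those for the primary outcome, and this is spelled out only as linear, proportional odds or logistic models by outcome type.
- **Covariates.** Expecting confounding from "factors such as age and time since diagnosis, we will account for these as covariates in the analyses", the plan adds that opiate use will be considered. No secondary outcome's own baseline appears.
- **Aim 3.** Change in GUPI, and PGI, are modelled with adjustment for baseline GUPI.

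The baseline values will exist. Under Clinical assessments (after section 5.6.3): "The battery of assessments below will be given at pretreatment, posttreatment, and at the three-month follow-up mark". The protocol table in Appendix O marks PHQ-8, GAD-7, PCL-5, CSQ-CAT, PROMIS-29 and the body map at pre-treatment. PGI is given only after treatment and at follow-up (section 5.7.1).

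**The concern.** Subtracting the baseline is not the same as adjusting for it. A change score fixes the slope of follow-up on baseline at 1. When the true slope is smaller, patients who start high tend to fall back, and a change-score comparison carries part of any chance baseline difference between arms into the treatment estimate. Putting the outcome's own baseline in the model estimates that slope and removes this component.

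Randomisation is stratified only by opioid use (section 5.3), so nothing in the design balances baseline distress or PROMIS-29 scores across arms of 50 and 25. The emotional distress comparisons depend entirely on these secondary models. Section 9.1 itself notes that appropriate covariate adjustment increases power, and an outcome's own baseline is usually the most useful covariate available.

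The plan's reference to approaches like the primary one does not clearly fill the gap. Carried over literally, the baseline entering the PHQ-8 or PCL-5 model would be baseline GUPI.

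**Working it through.** **Inputs from section 9.1.** "Assuming a Type I error of 0.05 and power of .90" (sidedness not stated; two-sided assumed); "A 7-point decrease in total GUPI score is considered clinically meaningful"; "standard deviation of 8.61"; 50 SM and 25 AC patients "with a 2:1 randomization scheme".

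**Assumptions, not in the documents.** Pre-post correlation rho of 0.3 to 0.8; equal baseline and follow-up SDs; an illustrative secondary effect of 0.5 SD; the body map scored as a count and treated as continuous. The variance formulas do not apply to the proportional odds or logistic models.

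**Step 1: reproduce the plan's figure.** The standardised effect is 7/8.61 = 0.813. A two-sided 5% t-test (noncentral t, 73 df) with 50 and 25 patients gives 90.6% power, so the stated 90% is reproduced. No power figure is given for any secondary outcome.

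**Step 2: variance of the treatment difference.** In units of the outcome variance, multiplied by (1/50 + 1/25) = 0.06:

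- change score: 2(1 − rho)
- own baseline as covariate: 1 − rho²
- ratio, adjusted to change: (1 − rho²) / [2(1 − rho)] = (1 + rho)/2

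The ratio is below 1 for every rho below 1.

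**Step 3: what the excess is.** 2(1 − rho) = (1 − rho²) + (1 − rho)². The second term is the chance baseline imbalance carried into the change-score estimate. The baseline difference between arms has standard error √0.06 = 0.245 SD, and the change score carries −(1 − rho) times the difference obtained.

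**Step 4: power for a 0.5 SD effect.** Noncentral t, two-sided 5%; effect divided by √[2(1 − rho)] with 73 df, or by √(1 − rho²) with 72 df.

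| rho | Variance, change | Variance, adjusted | Ratio | SE, change (SD) | SE, adjusted (SD) | Shift from a one-SE imbalance (SD) | Power, change | Power, adjusted |
|---|---|---|---|---|---|---|---|---|
| 0.3 | 1.40 | 0.91 | 0.65 | 0.290 | 0.234 | 0.17 | 39.9% | 56.0% |
| 0.5 | 1.00 | 0.75 | 0.75 | 0.245 | 0.212 | 0.12 | 52.2% | 64.3% |
| 0.7 | 0.60 | 0.51 | 0.85 | 0.190 | 0.175 | 0.07 | 73.9% | 80.5% |
| 0.8 | 0.40 | 0.36 | 0.90 | 0.155 | 0.147 | 0.05 | 89.0% | 91.9% |

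A simulation of 4,000 trials at rho 0.5 gave standard errors of 0.246 (change) and 0.215 (adjusted). The slope of the estimate on the baseline imbalance was −0.50 for change and about 0 for adjusted.

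**Step 5: would baseline GUPI do instead?** Suppose baseline GUPI correlates k with the outcome's own baseline and relates to follow-up only through it. It then recovers k² of the (1 − rho)² excess: 9% at k = 0.3 and 25% at k = 0.5 (k is assumed). Under that assumption, a literal carry-over of the primary covariate leaves most of the loss in place.

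**The case against.** The strongest reply is that the plan never says baseline will be left out. The secondary paragraph follows the primary model, which is baseline-adjusted, and says the methods will be similar. The natural analogue for PHQ-8 is baseline PHQ-8. The covariates are introduced as examples, so the list is open. Nor does the word change imply no adjustment here: Aim 3 models change in GUPI with baseline GUPI as covariate. In a linear model, change with own baseline as covariate gives the same treatment estimate and standard error as the follow-up value with that covariate. PGI, which has no baseline, sits in the same list of changes, so the word is used loosely.

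Much of this stands. A reader might infer that the sponsor has chosen an unadjusted change-score analysis; the documents do not establish that. What they do show is that the term is written in where GUPI is the outcome and is absent where the other scales are.

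Three further readings go beyond the text:

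- **That the GUPI subscales are analysed as change scores.** No change score is stated for them, so the figures above do not apply. All that is missing is a statement of which baseline enters.
- **That these are the trial's only comparisons on pain and quality of life.** GUPI total already covers pain and quality-of-life impact (section 5.7.1), and its baseline is handled.
- **That lost precision and baseline imbalance are two separate harms.** Step 3 shows they are the same quantity.

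It is also fair that Aim 2 seeks pilot data, that no secondary outcome is powered, and that the gain is small if the correlation is high.

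**Conclusion.** The concern holds for the continuous secondary outcomes, as a gap in specification with a real but assumption-dependent cost. As written, PHQ-8, GAD-7, PCL-5, CSQ, PROMIS-29 and the body map are examined as change with no own-baseline term, although every one has a baseline. If the analysis is run that way, the treatment-effect variance is 2/(1 + rho) times what it need be: 1.54, 1.33, 1.18 and 1.11 times at rho 0.3, 0.5, 0.7 and 0.8. For a 0.5 SD effect, the power given up is about 16, 12, 7 and 3 percentage points.

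A reader might also infer that the change-score estimates are biased. Over repeated randomisations they are not. The difficulty is conditional: given the imbalance that this one trial obtains, the estimate is shifted by (1 − rho) times it, and own-baseline adjustment removes the shift.

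The correlation, the effect size, equal SDs and two-sided testing are all assumptions. The direction of the precision result needs only equal SDs and rho below 1. The primary GUPI analysis is unaffected.

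**What to change.** Add to section 9.1 (Aim 2, secondary outcomes) wording to this effect:

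- Each continuous secondary outcome will be modelled as the post-treatment value (or, equivalently, the change) on treatment arm, that outcome's own baseline value and the covariates already listed; the adjusted SM minus AC difference will be reported.
- The GUPI pain and urinary subscale models will use the baseline score of the same subscale. This is a clarification.
- PGI has no baseline, so its model will use baseline GUPI, as Aim 3 already does.

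The cost is a few lines of analysis text and one degree of freedom per model. No new measurement, visit or patient is needed. Writing it down before analysis also removes a post hoc choice between change-score and adjusted models across several outcomes.

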10. FOLLOW UP-AND RECORD RETENTION

The study duration is estimated at four years. Data will be stored for five years after publication in de-identified form and informed consent forms will be kept for 3 years as per federal law. All data will be stored electronically where available. Information collected in databases may be archived indefinitely to support future research efforts.

Referred by: _____ Date: _____

Patient Name: _____
Patient MRN: _____

Please **circle** which ICD-10 Diagnosis for Interstitial Cystitis/Bladder Pain Syndrome this patient meets criteria for:

- N30.10 (without hematuria) or
- N30.11 (with hematuria)

Was this IC/BPS diagnosis made following a cystoscopy?

YES
 NO

Is this individual age 18+ and able to read, write, and understand English? (if YES, proceed)

Please indicate if this patient has any of the following (if YES to any of the items below, patient is not appropriate for this study):

- Comorbid neurological conditions including spinal cord injury or systematic neurologic illnesses, or central nervous system diseases such as brain tumor or stroke.
- Current or history of diagnosis of primary psychotic or major thought disorder within the past five years;
- Hospitalization for psychiatric reasons other than suicidal ideation, homicidal ideation, and/or PTSD (within the past 5 years);
- Psychiatric or behavioral conditions in which symptoms are unstable or severe (e.g. current delirium, mania, psychosis, suicidal ideation, homicidal ideation, substance abuse dependency) reported within the past six months;
- Current symptoms that would interfere with study participation, specifically active suicidal ideation with intent to harm oneself or active delusional or psychotic thinking;
- Difficulties or limitations communicating over the telephone;
- Any planned life events that would interfere with participating in the key elements of the study;
- Any active major medical issue that would preclude participation;
- Currently being treated for cancer;
- Cancer-related pain.
- Currently engaged in individual counseling/psychotherapy or unwilling to pause this treatment for the trial duration.

Does patient have access to a reliable internet connection?
(circle) YES NO

Is the patient interested in participating in this trial?

- YES
- NO

If yes, best # to

contact: Email:

Would you prefer a

call/text?

- CALL
- TEXT

13. APPENDIX B: TELEPHONE SCRIPT

TELEPHONE SCRIPT

Note to screening provider: prior to contacting a participant, please have a ‘screening form’ ready to fill out in corroboration with the individual’s responses to screening questions.

Mr/Ms. _____, my name is _____ and I work for Vanderbilt University Medical Center. You recently responded to an advertisement for a clinical study or we referred to us as an individual who has Interstitial Cystitis that may be interested in being a part of our project. The purpose of this phone call is to first tell you more about the study to see if you are interested in participating. If you are interested, I can then ask some questions to see if you are eligible to participate in the study. If you would like to proceed with the screening call, it will take approximately ten minutes. This call is strictly voluntary. Would you like to continue?

Yes, continue

No. May I call you back at a more convenient time?

- Yes. Schedule a time to call back.
- No. Thank you for your time. End phone call

This study is a clinical trial specifically for Interstitial Cystitis (IC). The purpose of this research study is to examine treatments for interstitial cystitis and to learn about different presentations of the condition. Participation involves three assessment visits, and either 8 additional weekly visits that will occur in person, online, or over the phone.

The assessment visits would occur in two parts, with the second being optional. Part 1 of the assessment would involve completing a series of questionnaires online. Part 2 would occur in-person and involve providing blood and urine samples, and undergoing testing that evaluates how your body assesses and responds to pain.

The weekly visits will either consist of speaking with a provider via telephone to monitor and discuss your symptom patterns week-by-week or to meet in person or online with a provider to enhance self-management of IC. We will provide compensation for the assessment visits and for travel expenses in some cases.

Do you think you may be interested in taking part in this research study?

- No. Thank them for their time and end phone call.
- Yes, continue.

Great. I would like to ask you some questions to see if you will be eligible for the study.

Can you please tell me your current age (if over 18, continue)?

Have you been diagnosed with Interstitial Cystitis/Bladder Pain Syndrome (IC/BPS)?

If not, then it does not appear that you qualify for the study. (Thank them for their time and end call) Note: if participant states they suspect they have interstitial cystitis but have not been formally diagnosed, continue and ask RICE screening questions.

Are you currently taking prescription medicines that are opiates?

- If YES, can you please tell me the name of the medicine and the dosage?
How often do you take the medicine, on average?

What state do you currently reside in? (Record answer)

Please answer yes or no to the following questions:

- Do you have a neurological condition or illness such as: spinal cord injury, general neurologic illness, brain tumor, or stroke?
- Have you ever experienced seeing things that other people cannot see or hearing things that other people cannot hear (within the past five years)?
- Have you had any psychiatric hospitalizations in the past 5 years? (Still eligible if PTSD or SI/HI.)
- Have you had any severe psychiatric or behavioral conditions in the past six months (e.g. current delirium, mania, psychosis, suicidal ideation, homicidal ideation, substance abuse dependency)?
- Do you speak English fluently?
- Do you have difficulties or limitations communicating over the telephone?
- Do you have any planned life events that would interfere with participating in the key elements of the study (e.g. participant would not be available for weekly appointments)?
- Are you experiencing any major medical issues at the moment?
- Are you currently undergoing cancer treatment?
- Are you experiencing any cancer-related pain?
- Are you currently engaged in individual counseling/psychotherapy? If so, are you willing to pause this treatment for the duration of the trial? (proceed if NO to individual psychotherapy or YES to willing to pause treatment)
- Are you experiencing any active thoughts of harming yourself or seeing/hearing things that are not there?

If YES: for support, please call the national suicide crisis hotline at [name] or visit www.suicidepreventionlifeline.org to chat online with support staff.

Note: Also contact the PI for follow-up with the individual and provide the individual with the PI's office number [contact].

If yes to any of the above (other than pausing psychotherapy for duration of trial and speaking English): it does not appear that you qualify for the study. Thank them for their time and end call (note: if patient endorses

suicidal ideation contact PI).

- Do you have a stable internet connection/access at home? (circle YES or NO, proceed regardless of answer)

If unsure about any of the above...I may need to ask some additional questions based on your responses today to see if you qualify for the study. Would it be possible for me to call you back with more information (note: contact PI to clarify as needed)?

If no to all of the above, proceed with questions regarding current symptoms: I'd like to ask you a few questions about your current symptoms:

[RESEARCH PERSONNEL MOVE TO RICE CRITERIA AND ASK QUESTIONS]

If qualified via RICE Questionnaire..... then it appears that you qualify to be in the study. Are you interested in taking part in this study?

- No. Thank you for your time.
- Yes. Great. Ask internet question:

Do you have a stable internet connection/access at home? (circle YES or NO, proceed regardless of answer; enrollment might be delayed if NO due to COVID-19, but they will be provided with more information in the future)

If patient does not have a stable internet connection: please inform the participant that due to COVID visitation restrictions we are conducting visits online and that potential study participation will need to be delayed. If this changes in the future we will contact the participant at that time.

Finally, provide available times for intake appointment and schedule with participant.

Note for individuals who are currently taking opiates: Please note that as [REDACTED] study evaluates how [REDACTED] body responds to pain, it is important to not take any medicines the day of the assessment that could change how [REDACTED] may or may not feel pain. If [REDACTED] are taking opiates, [REDACTED] ask that you do not take them before the assessment appointment. [REDACTED] will remind you about this closer to the date as well.

[REDACTED] are very much looking forward to meeting you and having you be a part of this project. Can you please provide me with the best number to reach you and an email address? To make things easier, we would like to remind you of your appointment in a way that best suits you. Can [REDACTED] please let us know if you would prefer a call or a text message?

IN-PERSON SCRIPT

Note to screening provider: prior to contacting a participant, please have a ‘screening form’ ready to fill out in corroboration with the individual’s responses to screening questions.

Hello [name].

My name is _____ and I work at Vanderbilt University Medical Center. We are conducting a new trial for Interstitial Cystitis/Bladder Pain Syndrome (IC/BPS) and would like to see if you are interested in participating.

The purpose of this discussion is to first tell you more about the study to see if you are interested in participating. I will ask you a brief set of questions about your current symptoms and medical experiences. If you are interested, I can then ask some questions to see if you are eligible to participate in the study. If you would like to proceed with our conversation, it will take approximately ten minutes. This discussion is strictly voluntary. Would you like to continue?

- If YES, proceed
- If NO, thank them for their time and end the conversation

This study is a clinical trial specifically for Interstitial Cystitis (IC). The purpose of this research study is to examine treatments for interstitial cystitis and to learn about different presentations of the condition. Participation involves three assessment visits, and either 8 additional weekly visits that will occur in person, online or over the phone.

The assessment visits would occur in two parts, with the second being optional. Part 1 of the assessment would involve completing a series of questionnaires online. Part 2 would occur in-person and involve providing blood and urine samples, and undergoing testing that evaluates how your body assesses and responds to pain.

The weekly visits will either consist of speaking with a provider via telephone to monitor and discuss your symptom patterns week-by-week or to meet in person or online with a provider to enhance self-management of IC. We will provide compensation for the assessment visits and for travel expenses in some cases.

Do you think you may be interested in taking part in this research study?

- **No.** Thank them for their time and end phone call.
- **Yes,** continue.

Great. I would like to ask you some questions to see if you will be eligible for the study.

Can you please tell me your current age (if over 18, continue)?

Have you been diagnosed with Interstitial Cystitis/Bladder Pain Syndrome (IC/BPS)?

If not, then it does not appear that you qualify for the study. (Thank them for their time and end call) Note: if participant states they suspect they have interstitial cystitis but have not been formally diagnosed, continue and ask RICE screening questions.

Are you currently taking prescription medicines that are opiates?

- If YES**, can you please tell me the name of the medicine and the dosage?
How often do you take the medicine, on average?

What state do you currently reside in? (record answer)

Please answer yes or no to the following questions:

- Do you have a neurological condition or illness such as: spinal cord injury, general neurologic illness, brain tumor, or stroke?
- Have you ever experienced seeing things that other people cannot see or hearing things that other people cannot hear (within the past five years)?
- Have you had any psychiatric hospitalizations in the past 5 years? (Still eligible if PTSD or SI/HI.)
- Have you had any severe psychiatric or behavioral conditions in the past six months (e.g. current delirium, mania, psychosis, suicidal ideation, homicidal ideation, substance abuse dependency)?
- Do you speak English fluently?
- Do you have difficulties or limitations communicating over the telephone?
- Do you have any planned life events that would interfere with participating in the key elements of the study (e.g. participant would not be available for weekly appointments)?
- Are you experiencing any major medical issues at the moment?
- Are you currently undergoing cancer treatment?
- Are you experiencing any cancer-related pain?
- Are you currently engaged in individual counseling/psychotherapy?
- If so, are you willing to pause this treatment for the duration of the trial? (must answer YES)
- Are you experiencing any active thoughts of harming yourself or seeing/hearing things that are not there?

If YES: for support, please call the national suicide crisis hotline at [name] or visit www.suicidepreventionlifeline.org to chat online with support staff.

Note: Also contact the PI for follow-up with the individual and provide the individual with the PI's office number [contact].

If yes to any of the above (other than pausing psychotherapy for duration of trial and speaking English): it does not appear that you qualify for the study. Thank them for their time and end call (note: if patient endorses suicidal

ideation contact PI).

If screening provider is unsure about any of the above...I may need to ask some additional questions based on your responses today to see if you qualify for the study. Would it be possible for me to call you back with more information (note: contact PI to clarify as needed)?

If no to all of the above, proceed with questions regarding current symptoms: I'd like to ask you a few questions about your current symptoms:

[RESEARCH PERSONNEL MOVE TO RICE CRITERIA ON SCORING FORM AND ASK QUESTIONS]

If qualified via RICE Questionnaire..... then it appears that you qualify to be in the study. Are you interested in taking part in this study?

- No. Thank you for your time.
- Yes. Great. Ask internet question:

Do you have a stable internet connection/access at home? (circle YES or NO, proceed regardless of answer; enrollment might be delayed if NO due to COVID-19, but they will be provided with more information in the future)

If patient does not have a stable internet connection: please inform the participant that due to COVID visitation restrictions we are conducting visits online and that potential study participation will need to be delayed. If this changes in the future we will contact the participant at that time.

Finally, provide available times for intake appointment and schedule with participant.

Note for individuals who are currently taking opiates: Please note that as our study evaluates how our body responds to pain, it is important to not take any medicines the day of the assessment that could change how we may or may not feel pain. If you are taking opiates, we ask that you do not take them before the assessment appointment. We will remind you about this closer to the date as well.

We are very much looking forward to meeting you and having you be a part of this project. Can you please provide me with the best number to reach you and an email address? To make things easier, we would like to remind you of your appointment in a way that best suits you. Can you please let us know if you would prefer a call or a text message?

